10.5.2 Safety objectives

10.5.2.1 Analysis set and grouping for the analyses

For all safety analyses, the Safety Set will be used. All listings and tables will be presented by patients and dose level throughout the overall observation period.

The overall observation period will be divided into three mutually exclusive segments:

1. pre-treatment period: from day of patient's informed consent to the day before first dose of study medication
2. on-treatment period: from day of first dose of study medication to the last dose of study medication
3. post-treatment period: up to day 30 after last eltrombopag administration

10.5.2.2 Adverse events (AEs)

Summary tables for adverse events (AEs) have to include only AEs that started or worsened during the on-treatment period, the **treatment-emergent** AEs (TEAEs). However, all safety data (including those from the pre-and post-treatment periods) will be listed and those collected during the pre-treatment and post-treatment period are to be flagged.

The incidence of TEAEs (new or worsening from baseline) will be summarized by system organ class and or preferred term, severity (based on CTCAE grades), type of adverse event, dose and relation to study treatment

Deaths reportable as SAEs and non-fatal serious adverse events will be listed by patient and tabulated by type of adverse event.

Specific safety event categories (SEC) will be considered. Such categories consist of one or more well-defined safety events which are similar and for which there is a specific clinical interest in connection with the study treatment(s).

For each specified SEC, number and percentage of patients with at least one event part of the SEC will be reported.

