8.1 Adverse events

8.1.1 Definitions and reporting

An adverse event is defined as the appearance of (or worsening of any pre-existing) undesirable sign(s), symptom(s), or medical condition(s) that occur after patient's signed informed consent has been obtained.

Abnormal laboratory values or test results occurring after informed consent constitute adverse events only if they induce clinical signs or symptoms, are considered clinically significant, require therapy (e.g., hematologic abnormality that requires transfusion or hematological stem cell support), or require changes in study medication(s).

Adverse events that begin or worsen after informed consent should be recorded in the Adverse Events CRF. Conditions that were already present at the time of informed consent should be recorded in the Medical History page of the patient's CRF. Adverse event monitoring should be continued for at least 30 days (or 5 half-lives, whichever is longer) following the last dose of study treatment. Adverse events (including lab abnormalities that constitute AEs) should be described using a diagnosis whenever possible, rather than individual underlying signs and

symptoms. When a clear diagnosis cannot be identified, each sign or symptom should be reported as a separate Adverse Event.

Adverse events will be assessed according to the Common Terminology Criteria for Adverse Events (CTCAE) version 4.03.

If CTCAE grading does not exist for an adverse event, the severity of mild, moderate, severe, and life-threatening, corresponding to Grades 1-4, will be used. CTCAE Grade 5 (death) will not be used in this study; rather, information about deaths will be collected through a Death form

The occurrence of adverse events should be sought by non-directive questioning of the patient (subject) during the screening process after signing informed consent and at each visit during the study. Adverse events also may be detected when they are volunteered by the patient (subject) during the screening process or between visits, or through physical examination, laboratory test, or other assessments. As far as possible, each adverse event should be evaluated to determine:

1. The severity grade (CTCAE Grade 1-4).
2. Its duration (Start and end dates or ongoing).
3. Its relationship to the study treatment
4. Action taken concerning study or investigational treatment (none, dose adjusted, temporarily interrupted, permanently discontinued, unknown, not applicable)

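### SAP section 9 gives no treatment-emergent window for adverse event tables, although the protocol limits them to first-to-last dose; the protocol's time segments also leave follow-up after efficacy stops unassigned

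*Protocol*

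**What the plan says.** Protocol 10.5.2.1 splits the observation period into three segments. The pre-treatment segment runs from consent to the day before the first dose. The other two are "on-treatment period: from day of first dose of study medication to the last dose of study medication" and "post-treatment period: up to day 30 after last eltrombopag administration". Protocol 10.5.2.2 then confines AE summary tables to the middle segment ("Summary tables for adverse events (AEs) have to include only AEs that started or worsened during the on-treatment period"). All safety data are listed, with pre- and post-treatment events flagged.

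Collection is wider than that window. Protocol 8.1.1 says "Adverse events that begin or worsen after informed consent should be recorded in the Adverse Events CRF" and "Adverse event monitoring should be continued for at least 30 days (or 5 half-lives, whichever is longer) following the last dose of study treatment".

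SAP 9 specifies the number of patients with at least one AE, the number of AEs per patient, and breakdowns of the total of AEs by term, seriousness, severity, AESI status, relationship, action and outcome. It uses the Safety Set and names no start date, end date, treatment-emergent definition or flag. SAP 10.7 sends the safety objective only to section 9 and to the withdrawal reasons in section 7.

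For patients who stop eltrombopag because of efficacy, Protocol 6.2.2 continues safety follow-up until all planned visits are complete. Protocol 6.1.2 allows the drug to be reintroduced after relapse.

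**The concern.** AE incidence is the main safety result of this single-arm study, and there is no control group against which a loose counting rule would cancel out. If the two documents count different events, the same data can give two incidences, and the choice could be made after results are seen.

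The periods in question matter clinically. Protocol 6.2.3 warns that platelet counts return to baseline within 2 weeks of stopping in most patients, with a raised bleeding risk. Protocol 8.1.3 makes bleeding an AESI. Under the protocol rule, a bleed after the last dose appears in a listing but in no incidence table. Under SAP 9 as written, a bleed during screening, before any drug, counts towards incidence; every patient enters with platelets below 20,000/µL.

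**Working it through.** **No AE rate to reproduce.** The documents state no expected AE rate. The only planning figure used is N = 33 (Protocol 10.7).

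**Step 1: the two rules side by side.**

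| Event timing | Protocol 10.5.2.2 summary tables | SAP 9 as written |
|---|---|---|
| Consent to day before first dose | Excluded; listed and flagged | Counted |
| First to last dose | Counted | Counted |
| Last dose to day 30 after | Excluded; listed and flagged | Counted |
| Beyond day 30, efficacy stop without restart | Excluded; listed, but no segment and so no stated flag | Counted |

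The Safety Set does not close the gap. It decides which patients are counted, not when their events occurred.

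**Step 2: effect per patient.** With all 33 treated, one patient whose only event of a type lies outside the window moves incidence by 1/33 = 3.0 points. Two patients move it 2/33 = 6.1, three 3/33 = 9.1, five 5/33 = 15.2.

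**Step 3: time left in no segment after an efficacy stop.** Inputs: Protocol 6.1.2 (complete response for at least 8 weeks, then stable counts for 8 weeks at a reduced dose) and the visit days in Table 7-1. Assumptions: the 8 weeks (56 days) are counted from the first count at complete-response level, each decision is taken at the next scheduled visit, and drug is not restarted. Unassigned days = end of follow-up − (stop day + 30), not below 0.

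| First count at CR level | Reduction visit | Stop | Follow-up to Day 283 | Follow-up to Day 253 |
|---|---|---|---|---|
| Day 8 or 15 | 71 | 141 | 283 − 171 = 112 | 253 − 171 = 82 |
| Day 22 or 29 | 85 | 141 | 112 | 82 |
| Day 43 or 57 | 113 | 169 | 283 − 199 = 84 | 253 − 199 = 54 |
| Day 71 or 85 | 141 | 211 | 283 − 241 = 42 | 253 − 241 = 12 |
| Day 113 | 169 | 253 | 283 − 283 = 0 | 0 |

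Both end days are shown because Table 7-1 puts the final visit at Day 283, while Protocol 7.2.3 ties that visit to 30 days after the last dose. Its timing for an efficacy stop is therefore unclear.

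**Step 4: restart.** Take a stop at Day 141 and a bleed at Day 155. If drug restarts at Day 169, the last dose falls after the bleed, so the bleed is on-treatment and enters the tables. If drug never restarts, Day 155 is 14 days after the last dose, so the bleed is post-treatment and stays out. The same event changes class because of something that happens later.

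**The case against.** **The SAP may inherit the protocol rule.** The protocol wording is mandatory, and SAP 9 sets no competing window and does not claim to replace it. There is slight textual support: the action-taken options in SAP 9 omit the not-applicable category of Protocol 8.1.1, which a pre-dose event would need. But SAP 9 also omits the unknown category, so the omission is not specific to pre-dose events. SAP 1 presents the plan as the methods for the final analysis, and nothing in section 9 points back to the protocol definition. What stands is that a difference in reported rates is possible, not certain.

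**Pre-dose inflation is limited.** Screening lasts at most 28 days, and "Conditions that were already present at the time of informed consent should be recorded in the Medical History page", so only new or worsening events would enter.

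**Efficacy stops may be rare or absent.** They need complete response in all three lineages, a dose reduction that is optional, and a further 8 stable weeks. All safety data are listed, so no event is lost. First-to-last dose is also a recognised convention, and the protocol summarises by dose, which might separate drug-free days; however, no zero-dose class is stated. The gap in the segments stands, for what may be a small subset.

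**Stronger readings that the documents do not support.**

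- A reader might infer that Protocol 10.5.2.1 contradicts 10.5.2.2, because it says "All listings and tables will be presented by patients and dose level throughout the overall observation period". This reads naturally as a general statement, followed by the segments and then a specific rule on which segment feeds the AE tables.
- A reader might infer that SAE tables have no window, because "Deaths reportable as SAEs and non-fatal serious adverse events will be listed by patient and tabulated by type of adverse event" repeats none. SAEs and safety event categories are AEs, so the opening rule of 10.5.2.2 covers their tables.
- A reader might infer that the window must run to the longer of 30 days and 5 half-lives. Protocol 8.1.1 sets that period for monitoring. The tabulation window is a choice of convention, and the documents give no half-life to turn it into days.

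**Conclusion.** The point holds as a mismatch between documents and a gap in the time segments. SAP 9 as written would count events that Protocol 10.5.2.2 excludes, and no other part of the SAP supplies a treatment-emergent table. The effect is 3.0 points per affected patient if 33 are treated. The number affected cannot be derived from the documents. The length of the extra recording period is patient-time, so it should not be read as a difference in event rates.

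After an efficacy stop without restart, 0 to 112 days (to Day 283) or 0 to 82 days (to Day 253) fall in no segment, assuming stops at scheduled visits. A drug-free gap counts as on-treatment only if drug is restarted. The two problems are alternatives rather than additive: the segments matter where the protocol rule governs, and pre-dose counting matters where SAP 9 is taken literally. Neither touches the primary endpoint or the sample size. It should be settled before the AE tables are produced.

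**What to change.** 1. In SAP 9, adopt the Protocol 10.5.2.2 window (onset or worsening from first to last dose) for the AE, SAE and AESI tables, and add the flagged pre- and post-treatment listings.
2. Tabulate pre-dose events and events after the last dose in separate tables, so that bleeding after discontinuation appears in a table as well as a listing.
3. Add an off-drug follow-up segment, from day 31 after the last dose to the last planned visit, for patients who stop for efficacy.
4. Flag each AESI bleed as on or off drug from the dosing dates, whether or not drug is later restarted.

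The data are already collected: AE start and end dates (Protocol 8.1.1) and the Dosage Administration Record (Protocol 6.5). No visit or assessment is added. The cost is a little more programming and a wording change to Protocol 10.5.2.1 for the new segment, which under Protocol 12.1 needs a written, approved amendment. Items 1, 2 and 4 need only SAP text.

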10.5.2.3 Laboratory abnormalities

For laboratory tests covered by the CTCAE version 4.03, the reporting team will grade laboratory data accordingly. For laboratory tests covered by CTCAE, a Grade 0 will be assigned for all non-missing values not graded as 1 or higher. Grade 5 will not be used.

For laboratory tests where grades are not defined by CTCAE version 4.03, results will be categorized as low/normal/high based on laboratory normal ranges.

The following summaries will be generated separately for hematology, biochemistry tests and urinary laboratory tests:

- Worst post-baseline CTCAE grade (regardless of the baseline status). Each patient will be counted only once for the worst grade observed post-baseline.
- Shift tables using CTCAE version 4.03 grades to compare baseline to the worst on treatment value.
- For laboratory tests where grades are not defined by CTCAE version 4.03, shift tables using the low/normal/high/ (low and high) classification to compare baseline to the worst on-treatment value.

In addition to the above-mentioned tables and listings, other exploratory analyses, for example figures plotting time course of raw or change in laboratory tests over time or box plots might be specified in the SAP and TLF shells.

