6.2.3 Anticipated risks and safety concerns of the study drug

Thrombotic/Thromboembolic complications

The risk of thromboembolic events (TEEs) has been found to be increased in patients with chronic liver disease treated with 75 mg eltrombopag once daily for two weeks in preparation for invasive procedures. Six of 143 (4%) adult patients with chronic liver disease receiving eltrombopag experienced TEEs (all of the portal venous system) and two of 145 (1%) patients in the placebo group experienced TEEs (one in the portal venous system and one myocardial infarction). Five of the 6 patients treated with eltrombopag experienced the thrombotic complication at a platelet count $>200 \times 10^9/L$ and within 30 days of the last dose of eltrombopag. Eltrombopag is not indicated for the treatment of thrombocytopenia in patients with chronic liver disease in preparation for invasive procedures. In eltrombopag clinical trials in ITP, TEEs were observed at low and normal platelet counts. Caution should be used when administering eltrombopag to patients with known risk factors for thromboembolism including but not limited to inherited (e.g. Factor V Leiden) or acquired risk factors (e.g. ATIII deficiency, antiphospholipid syndrome), patients with prolonged periods of immobilization, malignancies, contraceptives and hormone replacement therapy, surgery/trauma, obesity and smoking. Platelet counts should be closely monitored and dose modifications must be made in accordance with parameters provided in the protocol.

The risks of thromboembolism and any of the following complications versus the benefit of improved platelet counts must be evaluated by the Investigator for each patient with known risks of TEEs.

Risk of hepatotoxicity

Eltrombopag administration can cause hepatobiliary laboratory abnormalities, severe hepatotoxicity and potentially fatal liver injury. In the controlled clinical studies in chronic ITP with eltrombopag, increases in serum ALT, AST and bilirubin were observed. Hepatotoxicity should be monitored and eltrombopag should be discontinued if hepatobiliary abnormalities are observed as described in [section 6.2.1.2](#). Exercise caution when administering eltrombopag to patients with hepatic disease.

Ophthalmic changes

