Cataracts were observed in toxicology studies of eltrombopag in rodents but have not been reported at significant rates over control groups in human trials. In controlled studies in thrombocytopenic patients with HCV receiving interferon therapy (n = 1439), progression of pre-existing baseline cataract(s) or incident cataracts was reported in 8% of the eltrombopag group and 5% of the placebo group. Retinal hemorrhages, mostly grade 1 or 2, have been reported in HCV patients receiving interferon, ribavirin and eltrombopag (2% of the eltrombopag group and 2% of the placebo group). Hemorrhages occurred on the surface of the retina (preretinal), under the retina (subretinal), or within the retinal tissue. Ophthalmological examination (see [Section 7.3.2.8](#)[7.3.2.8](#)) should be performed at baseline, 24 weeks, and also at Final Visit (or Early Withdrawal). Eltrombopag continuation should be re-considered if suspected cataract development or worsening, or in case of retinal hemorrhages. In clinical trials of eltrombopag in SAA cataracts have not been reported. There is no evidence of cataracts in PGF.

Bone marrow reticulin formation and risk of bone marrow fibrosis

Eltrombopag may increase the risk for development or progression of reticulin fibers within the bone marrow. The relevance of this finding, as with other TPO-R agonists, has not been established yet.

If immature or dysplastic cells not linked to primary disease are observed, peripheral blood smears should be examined for new or worsening morphological abnormalities (e.g., teardrop and nucleated red blood cells, immature white blood cells) or cytopenia(s). If the patient develops new or worsening morphological abnormalities and cytopenia(s) not linked to primary disease, treatment with eltrombopag should be discontinued. A bone marrow biopsy must be considered, including staining for fibrosis.

Progression of existing myelodysplastic syndrome

TPO-R agonists are growth factors that lead to thrombopoietic progenitor cell expansion, differentiation and platelet production. The TPO-R is predominantly expressed on the surface of cells of the myeloid lineage. For this class of TPO-R agonists, there is a concern that they may stimulate the progression of existing hematopoietic malignancies such as myelodysplastic syndrome.

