In clinical studies with a TPO-R agonist, romiplostim and eltrombopag, in patients with MDS, cases of transient increases in blast cell counts were observed and cases of MDS disease progression to AML were reported.

In the CETB115AUS01T study, eltrombopag in combination with IST was assessed in patients with SAA. Published results indicate that clonal cytogenetic evolution with dysplastic changes occurred at a similar frequency compared to NIH historic experience with standard IST (10-15%) (Townsley et al., 2017). All patients should be monitored regularly for new or worsening morphological abnormalities or cytopenia(s), and may require bone marrow evaluation, as clinically indicated.

Eltrombopag should be discontinued in case of suspected myeloproliferation not linked to the primary disease or if there is a suspected myeloproliferation due to eltrombopag treatment.

Bleeding events after study drug discontinuation

Following discontinuation of eltrombopag, platelet counts return to baseline levels within 2 weeks in the majority of patients, which increases the bleeding risk and, in some cases, may lead to bleeding. Platelet counts should be monitored as per protocol following discontinuation of eltrombopag.

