7.2.1.1 Eligibility screening

Patients must meet all inclusion and exclusion criteria at Screening to be eligible to proceed to the treatment period of the study.

The platelet count needs to be <20,000/ μ L (mandatory) along with the ANC <1,000/ μ L and/or hemoglobin <100 g/L in a peripheral blood analysis on day +30 or beyond after allo-HSCT to qualify the patient for enrolment. Platelets, ANC and hemoglobin re-tests in a peripheral blood analysis will be required at Screening within 7 days prior to intended study Day 1, to allow sample time for results to be returned before administration of eltrombopag.

Patient eligibility will be confirmed by the investigative staff and captured within the source documents maintained at the site. This information will be made available during planned interim monitoring visits and compared against the clinical database for accuracy. Only when eligibility has been confirmed will the patient initiate the study treatment. Additionally, investigative site staff will enter patient information into the electronic case report form (eCRF), and automated queries will be generated for immediate resolution should patient eligibility be in question based on the patient information entered.

Re-screening of a previously screen failed patient will be allowed only once. A patient may be re-screened once if there are exclusionary medical condition at the Screening that may resolve and allow for re-screening. Some examples of re-screening reasons are listed below. In cases of re-screening, eligibility must be confirmed with Novartis.

- Laboratory value(s) out of range due to sampling error or that might be within range after medically-appropriate supplementation. (Note: Before screen failing and then re-screening the subject, efforts should be made to repeat the laboratory assessment(s) during the original initial screening phase).
- Vital signs and ECG abnormalities that can be stabilized.
- The patient has a medical condition that can be stabilized or resolved prior to the repeat screening attempt.

Patients who are rescreened must sign a new informed consent and they will be assigned with a new patient identification number. All required screening activities must be performed when the patient is rescreened for participation in the study.

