### 6.13 Laboratory evaluation

#### **HEMATOLOGY**

The continuous variables to be described are:

- Neutrophils (/µL)
- Platelet count (/µL)
- Hemoglobin (g/L)

In addition, it will be shown:

- Number of patients with <20000 platelets, <1000 neutrophils and <100 hemoglobin.
- Number of patients with <20000 platelets, <1000 neutrophils and >100 hemoglobin.
- Number of patients with <20000 platelets, >1000 neutrophils and <100 hemoglobin.

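### For platelets, the worst-grade and baseline-to-worst tables start at the floor, so they say almost nothing about late falls, falls after stopping or high counts

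*Protocol*

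**What the plan says.** Protocol 10.5.2.3 commits to two graded summaries for hematology. One is the worst post-baseline grade, whatever the baseline status: "Each patient will be counted only once for the worst grade observed post-baseline". The other is "Shift tables using CTCAE version 4.03 grades to compare baseline to the worst on treatment value". Tests that CTCAE does not grade are classed by laboratory range, with a class for patients who are both low and high. Time-course figures and box plots are mentioned only as something the SAP might specify. Under Protocol 10.5.2.1 the on-treatment period ends at the last dose.

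On entry, Protocol 7.2.1.1 states: "The platelet count needs to be <20,000" per microlitre, and this is mandatory. The second cytopenia may be neutrophils below 1,000/µL "and/or hemoglobin <100 g/L in a peripheral blood analysis on day +30 or beyond after allo-HSCT". SAP 6.13 accordingly expects patients who lack one of the two, for example "Number of patients with <20000 platelets, <1000 neutrophils and >100 hemoglobin".

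Protocol 6.2.3 names the count-related risks. In chronic liver disease, "Five of the 6 patients treated with eltrombopag experienced the thrombotic complication at a platelet count" above 200 × 10⁹/L. After stopping, "Following discontinuation of eltrombopag, platelet counts return to baseline levels within 2 weeks in the majority of patients", with a risk of bleeding. Table 6-2 has platelet action levels at 150,000 and 250,000/µL.

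SAP 10.7 meets the safety objective with the adverse event analysis and the reasons for withdrawal. The SAP describes blood counts at screening (6.13) and as efficacy (10.2), but has no laboratory safety table.

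**The concern.** A worst-value summary shows harm when patients start well and get worse. Here every patient starts with very low platelets, and the drug is meant to raise them. The platelet risks that the protocol describes are of other kinds: counts that rise too far, and counts that fall back after stopping. A late fall after recovery on drug matters as well. A table that holds only the lowest value cannot tell these courses apart.

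The counts are taken at every visit from week 1. What is at stake is whether the report shows how many patients passed the levels the protocol itself uses, how low recovered patients fell again, and what happened after the drug was stopped. The primary endpoint is not affected.

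**Working it through.** The plan states no figure on this point, so there is none to reproduce. The check applies the two planned rules to platelet counts.

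**Inputs**
- Baseline platelets below 20 × 10⁹/L in every patient (Protocol 5.1, criterion 3, and 7.2.1.1); 33 patients planned (Protocol 4.1).
- On-treatment counts at weeks 1, 2, 3, 4, 6, 8, 10, 12, 16, 20, 24, 30 and 36, which is 13 visits (Protocol 7.2.2.2 to 7.2.2.5).
- Assumption: platelets are graded in the low direction only, with grade 4 below 25, grade 3 below 50, grade 2 below 75 and grade 1 below a lower limit of 150 (× 10⁹/L). The documents cite CTCAE 4.03 without cut points.

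**Step 1: the worst value.** W = min(c₁, c₂, …, c₃₆), so W ≤ c₁, the week 1 count. A later fall to any value above c₁ leaves W unchanged. This needs no grading assumption.

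**Step 2: the grade.** A baseline below 20 is grade 4. One on-treatment count below 25 makes the worst grade 4 as well. A later fall below c₁ cannot change that, because no lower category exists.

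**Step 3: five illustrative courses, baseline 15 × 10⁹/L.**

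| Course | Week 1 | Maximum | Week 36 | Planned shift | Worst grade from week 16 |
|---|---|---|---|---|---|
| No response | 14 | 16 | 15 | 4 to 4 | 4 |
| Sustained recovery | 16 | 120 | 120 | 4 to 4 | 1 |
| Recovery, late fall | 16 | 120 | 10 | 4 to 4 | 4 |
| Overshoot | 16 | 300 | 150 | 4 to 4 | 0 |
| Overshoot, then fall | 16 | 300 | 10 | 4 to 4 | 4 |

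Both planned tables are the same for all five, and a count of 300 is itself grade 0. The maximum and the later minimum, taken together, separate all five. (Under Protocol 6.1.2 a non-responder leaves at week 16; the first row's grades do not change.)

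**Step 4: how many patients could leave the 4-to-4 cell.** Only those with every on-treatment count at or above 25. The documents do not give that share. Over an assumed range:
- 0%: 33 × 0 = 0
- 5%: 33 × 0.05 = 1.65
- 10%: 33 × 0.10 = 3.3
- 20%: 33 × 0.20 = 6.6

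**Step 5: after stopping.** The shift table ends at the last dose, so it excludes falls after the final dose. The worst post-baseline grade is not expressly limited in that way, but by step 2 it is already at grade 4.

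**Step 6: the other lineages.** Assumed cut points are grade 4 below 0.5, grade 3 below 1.0 and grade 2 below 1.5 × 10⁹/L for neutrophils, and grade 3 below 80 and grade 2 below 100 g/L for hemoglobin. The entry limits then correspond to grades 3–4 for neutrophils and 2–3 for hemoglobin. A patient may also enter at neutrophil grade 0–2 or hemoglobin grade 0–1, since only one of the two must be low. Worsening past the baseline grade can therefore show. Its timing cannot, nor can a fall back only to the baseline grade.

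**The case against.** The strongest reply is that the plan as a whole is not blind.
- Protocol 10.4.2 and 10.5.1 plan platelet descriptives at weeks 16, 24 and 36.
- SAP 10.2 gives lineage response at weeks 16, 20, 24, 30 and 36, and SAP 10.3 gives maintained response at weeks 24 and 36. Some late loss will show there.
- Under Protocol 8.1.1 and 8.1.2.1, a laboratory abnormality that requires a dose change or hold is an adverse event, so overshoot leading to action under Table 6-2 should be recorded.
- Bleeding and thromboembolic events are of special interest (Protocol 8.1.3), and SAP 8 shows the reasons for dose changes.
- Protocol 10.5.2.2 lists all safety data, and listings of 33 patients can be read.

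All of this stands. But these outputs give no number of patients above a platelet level, no lowest count after response and no summary after stopping. Protocol 10.5.2.2 also restricts its adverse event summary tables to on-treatment events.

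A reader might infer more than the documents support:
- **That all hematology tables are saturated.** Step 6 shows otherwise for neutrophils and hemoglobin.
- **That high counts are invisible under any coding.** If platelets were classed by laboratory range, the low-and-high class would catch counts above the local upper limit, though not at the protocol's own levels.
- **That nearly all minima fall in weeks 1–2.** Nothing in the documents says so. Transfusions are allowed, and a non-responder's minimum may come at any visit.
- **That thrombosis is tied only to high counts.** Protocol 6.2.3 also reports events at low and normal counts in ITP.
- **That a falling count alone is the marrow signal.** The protocol's wording is "If the patient develops new or worsening morphological abnormalities and cytopenia(s) not linked to primary disease", so both parts are needed.

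**Conclusion.** The point holds for platelets, and for the two tables in Protocol 10.5.2.3 rather than for the whole plan. All 33 patients start below 20,000/µL, and the worst value is capped by the week 1 count. The tables therefore cannot separate sustained recovery from recovery followed by a late fall, except in patients whose counts all stay outside the lowest grade from week 1. Under the assumed cut points and shares, that is 0 to 6.6 of 33. Falls after the last dose are outside the shift table by definition.

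The cap at week 1 and the end at last dose rest on the documents alone. The 4-to-4 result rests on a lowest grade that takes in counts below 25,000/µL, and the statement that high counts cannot show rests on grading in the low direction only. The wider gap is that the SAP carries none of these tables and none of the optional figures. This is an inexpensive improvement to safety reporting.

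**What to change.** Keep the CTCAE shift tables for neutrophils, hemoglobin and biochemistry, and write them into the SAP. For platelets, add to the SAP:

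1. Number and percentage of patients whose maximum post-baseline count exceeds 150,000, 200,000 and 250,000/µL, with the last count before each thromboembolic event listed. These are reporting categories taken from Table 6-2 and Protocol 6.2.3.
2. The lowest on-treatment count after first platelet response, by patient and summarised. The nadir itself is needed: a patient who goes from 80,000 to 22,000/µL never drops below the 20,000/µL partial-response threshold, so a count of lost responses would miss that fall.
3. Counts after stopping, from the Final Visit (Protocol 7.2.3) and the toxicity follow-up in Protocol 6.2.2 where available, set against the last on-treatment count and baseline.

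The cost is SAP wording and a few extra tables. No new data are needed, and no dosing rule changes.
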